^g Predose plasma PK at every dosing visit. Specific time points for PK and select laboratory Weeks 0 and 4 provided in [Table 6](#). Participants should stay in the clinic for 48 hours after the first and last doses to complete assessments.

- ^h Full physical examination includes (at a minimum): alertness and orientation, general appearance, skin, head, eyes, ears, nose, throat, lungs, cardiovascular, gastrointestinal, musculoskeletal, and neurologic systems. Symptom-directed physical examinations to be performed as necessary.
- ⁱ Height at Screening will be used for BMI calculations at all visits.
- ^j Vital signs will be taken with the participant in the supine position after ≥ 5 minutes of rest. Temperature, respiratory rate, and SpO₂ are measured once per time point. Blood pressure (systolic and diastolic) and pulse: measured ≤ 30 minutes pre-dose and 1 hr (± 10 min), 2 hr (± 10 min), 4 hr (± 20 min), 12 hr (± 1 hr) post dose on Day 1 and once at all other noted visits. Should additional post dose vital signs be collected per Site SOP, these should be captured in eCRF.
- ^k Continuous digital ECG monitoring for at least 48 hours from Day -1 through Day 2 and at least 24 hours through first day of last dose (Day 29); leads may be disconnected for ~ 20 minutes following 24 hours after the first dose to allow for participant cleansing. Additional triplicate 12-lead ECGs are specified in [Table 7](#). Note: only predose triplicate ECGs are required at Day 15. Participant must rest quietly for ≥ 5 minutes prior to triplicate ECGs.
- ^l For drug screen panel, see [Table 11](#) other screening tests.
- ^m Following the second dose (Week 2) all participants will be observed for safety evaluation in the clinic for at least 4 hours post study drug administration or per local SOP (whichever is longer).

Table 6 Plasma PK and Selected Laboratory Time Points (Period 2)

Study Day/Specific Time	Days 1, 15, 29	Days 1 and 29							Days 2 and 30		Days 3 and 31	Weeks 1 through 16
	Pre-dose	Post dose										
	≤ 30 min prior to dose ^b	30 min (± 5 min)	1 hr (± 5 min)	2 hr (± 5 min)	4 hr (± 10 min)	6 hr (± 10 min)	8 hr (± 10 min)	12 hr (± 10 min)	24 hr (± 30 min)	36 hr (± 4 hr)	48 hr (± 4 hr)	Visits 3 through 15
Plasma PK ^a	X	X	X	X	X	X	X	X	X	X	X	Every visit
CBC, CRP, fibrinogen, coagulation, albumin	X					X			X Day 2 only		X Day 3 only	Every visit
Complement	X			X	X	X			X Day 2 only		X Day 3 only	Weeks 1, 5, 6, and 8 only

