Cytokines ^c	X			X	X	X			X Day 2 only		X Day 3 only	Weeks 1, 5, 6, and 8 only

Abbreviations: CBC = complete blood count; CRP = C-reactive protein; PK = pharmacokinetic.

^a Sufficient plasma PK sample to cover both WVE-006 and potential metabolites. When applicable and feasible, PK blood sampling should follow evaluations of vital

signs and ECGs to reduce any impact on these measurements.

^b Pre-dose laboratory results are NOT required prior to dosing

^c Cytokines samples will be collected and analyzed for: IL-1 β , IL-6, IL-10, IL-12/23 (P40), IFN- γ , TNF- α , MCP-1, and MIP-1 β

Table 7 Triplicate ECG Assessment Time Points (Period 2)

Study Day/ Specific Time	Day 1			Days 1 and 29							Days 2 and 30	Day 3
	Pre-first dose			Post first and last doses								
	-45 min ±5 min	-30 min ±5 min	-15 min ±5 min	30 min ±5 min	1 hr ±5 min	2 hr ±5 min	4hr ±10 min	6hr ±10 min	8hr ±10 min	12hr ±10 min	24hr ±30 min	48hr ±4 hr
ECG ^a	X	X	X	X	X	X	X	X	X	X	X	X

Abbreviations: ECG = electrocardiogram

^a Digital ECG monitoring for at least 48 hours from Day -1 through Day 2 and at least 24 hours through first day of last dose (Day 29). Additional triplicate ECG measurements at the time points listed here.

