3 OBJECTIVES, ENDPOINTS, AND ESTIMANDS

Table 8 Study Objectives and Endpoints for WVE-006-001

Primary Objective:	Primary Endpoint:

 To evaluate the safety and tolerability of WVE-006 	
 Incidence of treatment emergent adverse events (TEAEs), related TEAE, severe TEAE, serious TEAE Changes in safety assessment parameters (i.e., physical exam, vital signs, clinical laboratory results, ECGs (including any changes to QTcF)) Tolerability based on incidence of discontinuation due to TEAEs
Secondary Objective:	Secondary Endpoints:

 To evaluate the PK of WVE-006 after a single dose in healthy participants To evaluate the PK of WVE-006 after multiple doses in healthy participants 	
 PK parameters of WVE-006 in plasma, including AUC_{inf}, AUC_{0-24h}, AUC_{0-48h}, AUC_{last}, C_{max}, t_{max} PK parameters of WVE-006 in plasma following the first and last doses, including AUC_{tau}, AUC_{0-24h}, AUC_{0-48h}, AUC_{last}, C_{max}, t_{max}
Exploratory Objectives:	Exploratory Endpoints:

 To evaluate urine excretion of WVE-006 	
 Ae, Ae%, and cumulative Ae% (cum Ae%) for parent drug, as well as potential metabolites in urine

Abbreviations: Ae=amount excreted; AUC=area under the curve; C=concentration; ECG=electrocardiogram; PK=pharmacokinetic; t=time; TEAE=treatment-emergent adverse event

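### Period 2 collects timed blood pressure and the 24 h and 48 h inflammatory samples after the first dose only, which leaves a limited gap in the repeat-dose safety data

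*Combined protocol and SAP*

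**What the plan says.** Section 3, Table 8 lists among the primary endpoints "Changes in safety assessment parameters (i.e., physical exam, vital signs, clinical laboratory results, ECGs (including any changes to QTcF". Period 2 gives three doses, on Days 1, 15 and 29, to up to 6 active and 2 placebo participants.

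**Vital signs.** Table 5 footnote j sets blood pressure and pulse before dosing and at 1, 2, 4 and 12 h "post dose on Day 1 and once at all other noted visits". It adds: "Should additional post dose vital signs be collected per Site SOP, these should be captured in eCRF". Table 5 marks vital signs on Days 15, 29, 30 and 31, so one reading is due on each. The footnote does not say whether the Day 15 and Day 29 readings come before or after the injection.

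**Laboratory tests.** The post-dose columns of Table 6 up to 12 h cover both Day 1 and Day 29. The 24 h and 48 h entries for the CBC/CRP/fibrinogen/coagulation/albumin panel, complement and cytokines are restricted to Day 2 and Day 3. PK blood in those same columns is drawn on Days 30 and 31 as well. At later visits, complement and cytokines are taken at "Weeks 1, 5, 6, and 8 only"; the CBC/CRP panel is taken at every visit.

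**Presence in the unit.** Footnote g: "Participants should stay in the clinic for 48 hours after the first and last doses to complete assessments". Footnote m, on dose 2: "Following the second dose (Week 2) all participants will be observed for safety evaluation in the clinic for at least 4 hours post" dosing, or longer under local procedures.

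**The concern.** Repeat dosing is what Period 2 adds to Period 1. With up to 6 active and 2 placebo participants, the placebo group is too small to be a useful reference at any single time point. The most informative contrast is each participant's own response to the first and last doses, and that needs the same measurements at the same times.

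Tables 6 and 7 largely provide this for PK and ECG. They do not provide it for blood pressure, or for the inflammatory tests after 6 h. A fall or rise in blood pressure within 12 h of dose 2 or 3, or an inflammatory response that develops after 6 h and settles before Week 5, could leave no scheduled measurement. It would then be absent from the laboratory maximum and minimum changes and from the vital-sign summary in Section 9.3.5.2. Section 7.1.1 makes clinically significant hypersensitivity a Period 2 individual stopping criterion, so reactions on re-dosing are already a concern of the protocol.

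**Working it through.** The plan gives no figure to reproduce; Section 9.1 says the sample size does not rest on hypothesis testing. The check is a count of scheduled post-dose times.

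**Step 1: times after first and last doses.** Inputs: Table 5 footnote j, Table 6, Table 7. Absent times are those scheduled after dose 1 but not after dose 3.

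| Measure | After dose 1 (h) | After dose 3 (h) | Matched (h) | Absent after dose 3 (h) |
|---|---|---|---|---|
| Timed blood pressure/pulse | 1, 2, 4, 12 (4) | none (0) | none | 1, 2, 4, 12 |
| CBC, CRP, fibrinogen, coagulation, albumin | 6, 24, 48 (3) | 6 (1) | 6 | 24, 48 |
| Complement | 2, 4, 6, 24, 48 (5) | 2, 4, 6 (3) | 2, 4, 6 | 24, 48 |
| Cytokines | 2, 4, 6, 24, 48 (5) | 2, 4, 6 (3) | 2, 4, 6 | 24, 48 |
| Triplicate ECG | 0.5, 1, 2, 4, 6, 8, 12, 24, 48 (9) | 0.5, 1, 2, 4, 6, 8, 12, 24 (8) | 0.5 to 24 | 48 |

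Outside the timed blood pressure/pulse series there is one vital-signs reading on each of Days 2 and 3 after dose 1 and on each of Days 30 and 31 after dose 3. Days 15 and 29 have one reading each, of unspecified timing.

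**Step 2: blood pressure in a full cohort of 8.**
- After dose 1: 8 × 4 = 32 timed post-dose readings, over 8 administrations.
- After doses 2 and 3: 0 timed readings, over 8 × 2 = 16 administrations.
- So 8 of 24 administrations carry a timed series.

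**Step 3: 24 h and 48 h inflammatory tests.** After dose 1: 8 × 2 = 16 sampling occasions. After dose 3: 0.

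**Step 4: length of the laboratory gap.** The last inflammatory sample after dose 3 is at 6 h on Day 29. The next is at Week 5, Day 36. Nominal interval from dosing: 36 − 29 = 7 days. With both visits at the far ends of their ±3-day windows: 39 − 26 = 13 days.

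**Step 5: after the proposed change.** For dose 3, timed blood pressure goes from 0 to 4 post-dose points, the CBC/CRP panel from 1 to 3, and complement and cytokines from 3 to 5 each. For dose 2, timed blood pressure goes from 0 to 3 points (1, 2 and 4 h).

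**The case against.** The strongest reply is that most of the first-versus-last-dose comparison is already there. Table 6 gives matched complement and cytokines at 2, 4 and 6 h and a matched CBC/CRP panel at 6 h. Table 7 takes triplicate ECGs "Post first and last doses" from 30 minutes to 24 h. Vital signs are read on Days 30 and 31, and adverse events are collected throughout. This stands, and it rules out three stronger readings.

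- A reader might infer that no within-participant comparison of first and last dose is possible. The matched times in Step 1 show otherwise.
- A reader might infer that an acute rise in pulse after dose 3 would go unmeasured. Eight post-dose triplicate ECG times and continuous recording of at least 24 h through Day 29 give heart rate. Blood pressure is what lacks timed data.
- A reader might infer that a Day 29 pre-dose ECG is missing, because the pre-dose columns of Table 7 are headed "Pre-first dose". The point is weak. Table 7 also omits the Day 15 pre-dose ECG that footnote k requires, Table 5 marks an ECG on Day 29, and Section 9.3.1 takes baseline before the Week 0 dose.

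It can also be said that the reduced sampling is explicit and so probably deliberate, that first and last doses are named in the PK endpoints only, and that Section 4.1.2 describes the Week 4 stay as being for PK. This is fair: the documents never set a first-versus-last-dose safety comparison as an aim. But the primary safety endpoint covers Period 2, and no reason is given for the asymmetry.

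Two other possible sources of data do not close the gap. Extra vital signs under site procedures are optional and need not be uniform across up to 4 units. The safety laboratory row of Table 5 was not legible in the text available, but footnote f sends the tests listed in Table 6 to the Table 6 schedule, and Table 11 does not include cytokines.

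**Conclusion.** The point holds in a limited form. Followed exactly, the schedule guarantees no blood pressure reading at a fixed time after doses 2 and 3, and no Table 6 inflammatory sample between 6 h after dose 3 and Week 5. Blood pressure change within 12 h of those doses, and inflammatory change confined to that interval, cannot be compared with dose 1. They reach the primary safety summaries only if an untimed, optional or unscheduled measurement happens to catch them.

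The laboratory part matters only if a response can arise after 6 h and resolve before Week 5. The documents give no kinetics for these markers, so that is an assumption. The counts assume a full cohort of 8 and all three doses given. This is a worthwhile, inexpensive improvement; the gap does not invalidate Period 2.

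**What to change.** 1. Table 5 footnote j: apply the Day 1 blood pressure and pulse set (pre-dose, 1, 2, 4 and 12 h) to Day 29. Apply the pre-dose, 1, 2 and 4 h readings to Day 15, inside the 4-hour observation already planned.
2. Table 6: remove the Day 2 and Day 3 restrictions, so that the CBC/CRP panel, complement and cytokines are also drawn with the Day 30 and Day 31 PK samples.
3. Section 9.3.5.2, or the separate SAP that Section 9 announces: show Day 29 to 31 values beside Day 1 to 3 values at matched times, descriptively and without testing.

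Cost: 5 readings on Day 29 plus 4 on Day 15 replace 2 single readings, a net 7 per participant, or 7 × 8 = 56 in a full cohort. Laboratory work rises by 2 sampling occasions per participant, 2 × 8 = 16 in all, at existing venepunctures. The downside is slightly more blood volume, assays and data entry, plus a schedule amendment. If the asymmetry is intended, the protocol should state the reason.

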2 INTRODUCTION

2.1 Study Rationale

WVE-006 is an oligonucleotide that was designed to specifically edit the Serpin Family A Member 1 (*SERPINA1*) mutant (Z) messenger ribonucleic acid (mRNA) back to wildtype (M). Editing of the *SERPINA1*-Z mRNA back to wildtype is expected to increase the concentration of M alpha-1 antitrypsin (M-AAT) protein in the serum and decrease the accumulation of Z-AAT in the liver, thus addressing both the lung and liver disease manifestations associated with Alpha-1 antitrypsin deficiency (AATD).

WVE-006 is not expected to have pharmacological activity in healthy volunteers (HV) since they do not have the Serpin Family A Member 1 (*SERPINA1*) mutation.

2.2 Background

AATD is a rare and clinically underrecognized condition that can affect the lung, liver, and rarely the skin. This disease can cause chronic obstructive pulmonary disease (COPD), a progressive, life-threatening lung disease, which results in severe shortness of breath, wheezing, chronic cough, and sputum production. In addition, these patients may present with asthma, chronic lung disease, emphysema, recurring chest infections, bronchitis, and bronchiectasis. AATD can also cause life-threatening liver disease, skin problems (panniculitis), and inflammation of the blood vessels (vasculitis). There are currently very limited treatment options for AATD, most of which are based on symptom management.

AATD is caused by pathogenic variants in the *SERPINA1* gene and is inherited in an autosomal and codominant manner, indicating that the two alleles are active and contribute to the genetic trait ([Greene et al., 2016](#)). The M allele is the most common allele of the alpha-1 gene and produces normal levels of M-AAT. The Z allele is the most common variant of the gene and results in 95% of severe cases of AATD ([Strnad et al., 2020](#)). The Z mutation of the *SERPINA1* gene results from a G-to-A missense mutation corresponding to a glutamic acid to lysine amino acid change at position 342 in the protein. The Z-AAT protein is misfolded and prone to aggregation in hepatocytes in a gain of function toxicity in the liver (which may lead to fibrosis, cirrhosis, or increased risk of hepatocellular carcinoma) and decreases the secretion of functional AAT into serum, resulting in a loss of functional AAT in the lung ([Strnad et al., 2020](#)).

WVE-006 is an investigational A-to-I editing oligonucleotide (AIMer) that was designed to specifically edit the *SERPINA1*-Z RNA back to wildtype.

2.3 Benefit/Risk Assessment

The information generated by this study will provide a better understanding of the study drug's safety profile and how it is distributed through and works in the human body. No significant toxicity is expected in treated participants since WVE-006 is targeted to mutant *SERPINA1*-Z RNA which will not be present in the study population. Only participants with wild type PI*MM

are included; this genotype contains 2 normal M alleles indicating that the participant does not have AATD. There may be unforeseen risks or toxicities since this will be the first time WVE-006 is administered to humans.

The WVE-006 Investigator's Brochure (IB) will be provided to the Investigator.

2.3.1 Risk Assessment

Nonclinical studies conducted in mice and monkeys yielded no toxicologically meaningful findings that would prevent initiation of clinical studies in HV or AATD patients.

CCI

CCI

2.3.2 Benefit Assessment

Since all participants will be HV without the *SERPINA1-Z* mutation, no direct benefits are expected for study participants. The knowledge gained from this testing may help to further develop WVE-006 as an effective treatment for patients with AATD.

2.3.3 Overall Benefit-Risk Conclusions

Risks to participants in this study have been minimized by the comprehensive safety assessments and the systematic review of safety data by the Data Monitoring Committee (DMC), and as such the risks are justified by the anticipated benefits that may be eventually afforded to patients with AATD.

3 OBJECTIVES, ENDPOINTS, AND ESTIMANDS

Table 8 Study Objectives and Endpoints for WVE-006-001

Primary Objective:	Primary Endpoint:

 To evaluate the safety and tolerability of WVE-006 	
 Incidence of treatment emergent adverse events (TEAEs), related TEAE, severe TEAE, serious TEAE Changes in safety assessment parameters (i.e., physical exam, vital signs, clinical laboratory results, ECGs (including any changes to QTcF)) Tolerability based on incidence of discontinuation due to TEAEs
Secondary Objective:	Secondary Endpoints:

 To evaluate the PK of WVE-006 after a single dose in healthy participants To evaluate the PK of WVE-006 after multiple doses in healthy participants 	
 PK parameters of WVE-006 in plasma, including AUC_{inf}, AUC_{0-24h}, AUC_{0-48h}, AUC_{last}, C_{max}, t_{max} PK parameters of WVE-006 in plasma following the first and last doses, including AUC_{tau}, AUC_{0-24h}, AUC_{0-48h}, AUC_{last}, C_{max}, t_{max}
Exploratory Objectives:	Exploratory Endpoints:

 To evaluate urine excretion of WVE-006 	
 Ae, Ae%, and cumulative Ae% (cum Ae%) for parent drug, as well as potential metabolites in urine

Abbreviations: Ae=amount excreted; AUC=area under the curve; C=concentration; ECG=electrocardiogram; PK=pharmacokinetic; t=time; TEAE=treatment-emergent adverse event

4 STUDY DESIGN

4.1 Overall Study Design

This is a double-blind, placebo-controlled, single ascending dose (SAD) and multidose Phase 1 study to assess the safety, tolerability, and PK of WVE-006 in healthy participants. Participants will be randomized to WVE-006 or placebo.

Period 1 will evaluate single ascending doses of WVE-006 in up to five cohorts of up to 8 healthy participants each (3:1 active:placebo). An additional cohort (Cohort 6) may be included to evaluate concentration-QTc. Participants may be on-study for up to 12 weeks. A sentinel strategy will be employed for the first 2 participants (1 active:1 placebo) of every new dose level during the SAD portion (Period 1) and in the multiple dose portion (Period 2) of the study, with a 48-hour observation period to assess for acute safety events. The Dose Escalation Committee (DEC) and the DMC will review available data through Day 8 that will include key PK parameters and safety for each dose cohort, as well as previously accumulated safety data and available PK data, to recommend subsequent dose escalation. Additional details are provided in [Section 4.1.2](#).

Dose Escalation Stopping Criteria (Period 1):

Dose escalation will be paused until further evaluation by the DMC if any of the following criteria are met. If it is confirmed that a stopping criterion was met, no further dosing will take place until after submission and approval of a substantial amendment if the DMC recommends the trial can continue.

- One or more at least possibly related Common Terminology Criteria for Adverse Events (CTCAE) Grade ≥ 3 TEAE or CTCAE grade ≥ 3 laboratory abnormality in a single cohort.
 - All grade 3 toxicities for vital signs must be confirmed with a repeat measurement obtained within 1 hour.
 - All grade 3 toxicities for laboratory parameters must be confirmed with a repeat measurement obtained within 24 hours.
- Two or more at least possibly related CTCAE grade ≥ 2 TEAEs or CTCAE Grade ≥ 2 laboratory abnormalities in a single cohort.
 - All grade 2 toxicities for vital signs must be confirmed with a repeat measurement obtained within 1 hour.
 - All grade 2 toxicities for laboratory parameters must be confirmed with a repeat measurement obtained within 24 hours.
- Any at least possibly related SAE in a single cohort.

In Period 2, a single cohort of up to 8 healthy participants including up to 6 WVE-006 and 2 placebo treated participants (3:1 active:placebo) will receive multiple doses of WVE-006. Participants may be on-study for up to 16 weeks. The DEC and DMC will review available

safety and PK data from Period 1 to select the maximum tolerated dose level (MTD) or other selected dose achieved if MTD was not reached. Additional information about treatment is provided in [Section 4.1.2](#). Individual treatment stopping criteria for participants in Period 2 are in [Section 7.1.1](#).

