Dose escalation will be paused until further evaluation by the DMC if any of the following criteria are met. If it is confirmed that a stopping criterion was met, no further dosing will take place until after submission and approval of a substantial amendment if the DMC recommends the trial can continue.

- One or more participants experiencing at least possibly related Common Terminology Criteria for Adverse Events (CTCAE) Grade ≥ 3 TEAE or CTCAE grade ≥ 3 laboratory abnormality in a single cohort.
 - All grade 3 toxicities for vital signs must be confirmed with a repeat measurement obtained within 1 hour.
 - All grade 3 toxicities for laboratory parameters must be confirmed with a repeat measurement obtained within 24 hours.
- Two or more participants experiencing at least possibly related CTCAE grade ≥ 2 TEAEs or CTCAE Grade ≥ 2 laboratory abnormalities in a single cohort.
 - All grade 2 toxicities for vital signs must be confirmed with a repeat measurement obtained within 1 hour.
 - All grade 2 toxicities for laboratory parameters must be confirmed with a repeat measurement obtained within 24 hours.
- One or more participants experiencing any at least possibly related SAE in a single cohort.

Period 2 Individual Stopping Criteria:

Dosing will be paused or discontinued (per Investigator judgment) for an individual participant at any time in the study if:

- Participant experiences any severe or serious adverse event considered at least possibly related to study drug.
- Participant experiences, in the Investigator's opinion, clinically significant hypersensitivity to WVE-006 (or placebo) administration.
- Participant has any medical condition that is judged by the Investigator to jeopardize the participant's safety if he or she continues to receive the study drug.

On discontinuation of treatment, participants will be encouraged to continue follow-up for safety per protocol. Per Investigator judgment with consultation with the Sponsor, the participant may be allowed to resume participation in the study if/when the event has resolved.

Sponsor: Wave Life Sciences UK Limited	Investigational Product: WVE-006	Developmental Phase: Phase 1	IRAS ID Number: 1008635

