4.1.2 Treatment

Period 1: Single Ascending Dose

Period 1 will evaluate single ascending doses of WVE-006 in up to five cohorts of up to 8 healthy participants each. Each cohort will include up to 6 WVE-006-treated and 2 placebo-treated participants (3:1 active:placebo). Participants will receive a single SC dose of WVE-006 or placebo on Day 1.

CCI

A sentinel strategy will be employed for the first 2 participants (1 active, 1 placebo) of every new dose level during the SAD portion of the study. The sentinel participants will be dosed and monitored in the clinic for 48 hours to identify any potential acute safety events. If neither of these sentinel participants experiences stopping criteria and if there are no other safety concerns during this 48-hour period, the remaining 6 participants will be randomized in a blinded fashion to active study drug (n=5) or placebo (n=1) and may be dosed on the same day. These participants will be observed in clinic for 48 hours after administration of study drug. Participants will attend weekly clinic visits on Weeks 0 through 12 to be followed for safety, tolerability, and PK assessments through Day 85 per the SoA.

If Period 1 Dose Escalation Stopping Criteria (see [Section 4.1](#)) are met at any point, dosing will be paused until further review and confirmation by the DMC. No further dosing will take place until after submission and approval of a substantial amendment if the DMC recommends the trial can continue.

Period 2: Multiple Doses

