In Period 2, a single cohort of up to 8 healthy participants, including up to 6 WVE-006 and up to 2 placebo treated participants (3:1 active:placebo), will participate in a multidose assessment of WVE-006. A sentinel strategy will be employed for the first 2 participants (1 active:1 placebo), with a 48-hour observation period to assess for acute safety events. The DEC and DMC will review available safety and PK data from Period 1 to select the MTD with an acceptable PK profile. The MTD is defined as the dose below a dose level where any of the dose escalation stopping rules were met. If MTD is not achieved in Period 1 (i.e., no dose escalation stopping rules were met and all doses were well tolerated), then the highest dose reached in Period 1 will likely be selected for Period 2, though the DEC and DMC may select a lower dose based on all available information. At least 4 weeks of safety data for the proposed dose and all available data from the study must be available from Period 1 in order to inform the DEC and DMC Period 2 dose selection. WVE-006 or placebo will be administered every other week (Q2W) over 4 weeks (total of 3 doses; Weeks 0, 2, and 4). Following the first dose (Week 0) and last dose (Week 4), participants will stay in the clinic for at least two nights for PK assessments. Following the second dose (Week 2) all participants will be observed for safety evaluation in the clinic for at least 4 hours post-study drug administration or per local SOP (whichever is longer).

In Period 2, dosing will be paused or discontinued (per Investigator judgment) for an individual participant; see [Section 7.1.1](#) for additional details.

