4.3 Justification for Dose

Initial Dose

As described in the International Council for Harmonization (ICH) M3(R2) guideline, the selection of the first-in-human (FIH) dose and dose escalation plan will not be higher than that supported by NOAELs from the 5-week interim data of the GLP 13-week repeat dose toxicity studies in mice and cynomolgus monkeys. Selected doses were based on the totality of the data for both mouse and cynomolgus monkey, including the NOAEL provided by the GLP toxicity studies, projected pharmacologically active dose and assessment for potential QTc prolongation risks. The initial dose was selected using the most relevant approaches described in:

- US Food and Drug Administration (USFDA) guidance for industry: [Estimating the Maximum Safe Starting Dose in Initial Clinical Trials for Therapeutics in Adult Healthy Volunteers](#) (2005).
- European Medicines Evaluation Agency (EMA) [Guideline on strategies to identify and mitigate risks for first-in-human and early clinical trials with investigational medicinal products](#) (2017)

CCI [REDACTED] Two interspecies scaling approaches were used for HED and safety margin projection, a conservative approach based on body surface area (BSA) scaling ([FDA, 2005](#)), as well as an empirical approach based on body weight supported by literature, which showed a 1:1 body-weight-based conversion factor from monkey to human and an approximately 1:7 body-weight-based conversion factor from mouse to human for plasma exposure ([Nanavati et al., 2021](#); [Wang et al., 2019](#)).

The pharmacological activities of WVE-006 are not expected in HV CCI [REDACTED]

Dose Escalation

CCI

The planned initial dose for Period 1 is 30 mg (Period 1, Cohort 1). Subsequent dose levels will be determined by the DEC and DMC based on previous Period 1 cohort data and will not exceed a CCI increase of the prior dose. The maximum dose will not exceed the limit specified in [Section 4.1.2](#). Dosing decisions will be communicated directly to the site.

CCI

If adequate safety and tolerability is observed in the initial dose cohorts (Cohorts 1 to 5) and no cohort stopping criterion was met, an optional cohort (Cohort 6) may be conducted in order to characterize the safety, tolerability, PK and the relationship between drug concentration and QTc prolongation at an appropriate dose.

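### Period 1 stopping criterion 2 counts participants in the synopsis but events in Section 4.1, so one participant with two related grade 2 events halts dosing under one wording and not the other

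*Combined protocol and SAP*

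**What the plan says.** Section 4.1 sets the second Period 1 stopping criterion as "Two or more at least possibly related CTCAE grade ≥ 2 TEAEs or CTCAE Grade ≥ 2 laboratory abnormalities in a single cohort". The synopsis in Section 1.1 begins the same criterion with "Two or more participants experiencing at least possibly related CTCAE grade ≥ 2 TEAEs" and then extends it to laboratory abnormalities of the same grade. Both are current text, and the confirmation rules for repeat measurements match.

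The first criterion shows the same change of unit: "One or more participants experiencing at least possibly related Common Terminology Criteria for Adverse Events (CTCAE) Grade ≥ 3 TEAE" in the synopsis and "One or more at least possibly related Common Terminology Criteria for Adverse Events (CTCAE) Grade ≥ 3 TEAE" in Section 4.1. The third, on related SAEs, does too.

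Section 4.1.2 refers back to Section 4.1 and says that if the criteria "are met at any point, dosing will be paused until further review and confirmation by the DMC". A confirmed criterion stops dosing until a substantial amendment has been approved. The criteria also serve three other purposes:

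- **Sentinel check** (synopsis and Section 4.1.2): the other six participants may be dosed "If neither of these sentinel participants experiences stopping criteria and if there are no other safety concerns during this 48-hour period".
- **Period 2 dose** (Section 4.1.2): "The MTD is defined as the dose below a dose level where any of the dose escalation stopping rules were met".
- **Optional cohort** (Section 4.3): given adequate safety and tolerability and if "no cohort stopping criterion was met, an optional cohort (Cohort 6) may be conducted".

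**The concern.** A stopping rule has to give one answer for any set of data. Here the protocol holds two complete statements of the same rule with different counting units, and it neither says which prevails nor defines the unit. The rule in Section 9.3.5.1 that counts a repeated event once applies to adverse event summaries, not to stopping decisions.

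The disputed case is realistic. Laboratory abnormalities count in their own right, and the chemistry panel in Section 10.2 contains tests that tend to move together (ALT, AST, GLDH, bilirubin). One volunteer with a coherent liver signal could produce two grade 2 findings while nobody else in the cohort has any.

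In that case the two texts disagree on whether healthy volunteers continue to be dosed in a first-in-human study, on which dose is the MTD, and on whether the Cohort 6 condition holds. At the sentinel step, a single active sentinel can meet the criterion alone under Section 4.1. Under the synopsis it cannot, because the placebo sentinel would also need a qualifying event. Up to four research units may be working from these texts.

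**Working it through.** **Where the two forms differ.** Call a related grade 2 or higher TEAE or laboratory abnormality a qualifying event. Two affected participants imply at least two events, so every cohort that meets the synopsis form also meets the Section 4.1 form. Enumerating 0 to 3 qualifying events in each of three participants, the rules disagree only in the patterns (2,0,0), (3,0,0) and their permutations: one affected participant with two or more events and nobody else affected. If any of those events is grade 3 or higher, or a related SAE, criterion 1 or 3 stops dosing under both texts. Criteria 1 and 3 have a threshold of one, so counting people or events gives the same result. Only criterion 2 is affected.

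**Inputs for size.** Cohort size comes from the protocol: up to 8, of whom 6 are on active drug. The documents give no event rates, so two quantities are assumed:

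- p, the chance that a participant has at least one qualifying event: 5% or 10%.
- q, the share of those participants with two or more: the value implied by independent (Poisson) events, or 25% to represent clustering.

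**Formulas.** With n participants at risk:

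- Participant unit: 1 − (1−p)^n − n·p·(1−p)^(n−1)
- Event unit: 1 − (1−p)^n − n·p·(1−q)·(1−p)^(n−1)
- Gap: n·p·q·(1−p)^(n−1)
- Independence: λ = −ln(1−p) and q = 1 − λ(1−p)/p. This gives λ = 0.0513, q = 0.0254 at p = 5%, and λ = 0.1054, q = 0.0518 at p = 10%.

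**Worked case, n = 8, p = 5%.** (0.95)^8 = 0.6634 and 8 × 0.05 × (0.95)^7 = 0.2793. Participant unit: 1 − 0.6634 − 0.2793 ≈ 0.057. Gap: 0.2793 × 0.0254 = 0.0071. Event unit: about 0.064.

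**Chance per cohort of meeting criterion 2**

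| At risk | p | Participant unit | Event unit, independent | Gap, independent | Gap, q = 25% |
|---|---|---|---|---|---|
| 8 | 5% | 5.7% | 6.4% | 0.7 points | 7.0 points |
| 8 | 10% | 18.7% | 20.7% | 2.0 points | 9.6 points |
| 6 (active only) | 5% | 3.3% | 3.9% | 0.6 points | 5.8 points |
| 6 (active only) | 10% | 11.4% | 13.3% | 1.8 points | 8.9 points |

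A Poisson simulation of 1,000,000 cohorts agrees with the independent columns to within 0.1 point. With p from 5% to 20% and q of 20% or 50%, the same formula gives gaps of about 5 to 20 points, so the result depends heavily on q.

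**Sentinel step.** If only the active sentinel can have a qualifying event, the participant unit gives 0 and the event unit gives p·q: 0.1% to 0.5% under independence and 1.3% to 2.5% at q = 25%. These figures apply the cohort value of p to a 48-hour window, so they are too high unless all qualifying events are acute.

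The cohort gaps are upper bounds for the effect on overall stopping, because some of the participants concerned would meet criterion 1 or 3 anyway.

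**The case against.** The strongest reply is that the conflict is narrow and the protocol already leans the safe way. Section 4.1.2 cites Section 4.1, which is the stricter form. The halt until amendment needs confirmation by an independent, unblinded DMC that also reviews each cohort before escalation. The sentinel check separately requires that there be no other safety concern, and a sentinel with two confirmed related grade 2 events within 48 hours would probably fail on that ground. Cohort 6 is optional, and the committees may choose a lower Period 2 dose. All of this stands and limits the practical risk.

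It does not remove the contradiction. A cross-reference is not a statement of precedence, and the synopsis sets out the rule in full. The DMC is asked to confirm whether a criterion was met, and the protocol gives it two tests. Section 10.5.2 requires adherence to everything the protocol defines, so continuing to dose in the disputed case would breach Section 4.1 while satisfying the synopsis.

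Two further points are fair. The documents do not show which unit was intended; the synopsis uses participants in all three criteria, so Section 4.1 may be a shortened form of it. And the sentence can be read so that relatedness qualifies only the TEAEs and not the laboratory abnormalities. Neither reading reconciles the two texts. The DEC and DMC charters were not available; they may specify a unit, but they would not correct the protocol.

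**Conclusion.** The concern holds. Criterion 2 has two different thresholds in current text, and they give opposite answers when the only affected participant in a cohort has two or more qualifying grade 2 events and criteria 1 and 3 are not met. This conclusion rests on the wording alone and needs no assumed rate.

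The size is unknown. The range of 0.6 to 2.0 points per cohort assumes independent events with p of 5% to 10%. The range of 5.8 to 9.6 points assumes q = 25%, and clustering is the more natural picture for linked liver tests. Nothing in the documents fixes either quantity.

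The point must be fixed despite its narrowness. It is a decision threshold in a first-in-human study, it governs a halt that only a substantial amendment can lift, and it should not be settled after the event has occurred.

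**What to change.** The sponsor should confirm the intended unit and put identical wording for criterion 2 in Sections 1.1 and 4.1. The text should state how several findings in one participant count, covering both two different tests and the same test abnormal at successive visits. The DEC and DMC charters should then be aligned.

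- If events are intended, amend the synopsis.
- If participants are intended, amend Section 4.1 to count participants and give the reason, because this relaxes the form that Section 4.1.2 now cites.

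Until this is settled, apply the stricter Section 4.1 wording, including at the sentinel check. That interim rule is advice; the documents do not state it.

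The cost is a wording amendment in one or two places, with no added participants or procedures. Keeping the event unit brings a somewhat higher chance of a pause, on the scale given in the working.
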